4 STUDY OBJECTIVES AND ENDPOINTS

Objective	Endpoint
Primary	
Efficacy: To evaluate the efficacy of omadacycline in adult subjects with NTM pulmonary disease caused by MABC based upon subject assessment of symptoms	
Including but not limited to:
 
• Clinical response at Day 84 defined as improvement in severity of at least 50% of the symptoms present at baseline• Clinical response at Day 84 defined as improvement in severity of at least 50% of the symptoms present at baseline and no deterioration in severity of symptoms present at baseline
Safety: To evaluate the safety and tolerability of omadacycline in adult subjects with NTM pulmonary disease caused by MABC	
• Incidence of adverse events (AEs) and serious adverse events (SAEs)• Change from baseline for:
o Clinical laboratory parameterso Vital signso Electrocardiograms (ECGs)• Incidence of potentially clinically significant:
o Clinical laboratory parameterso Vital signso ECGs

[figure not shown]
Secondary	
To evaluate patient-reported outcomes (PROs) and quality of life in adult subjects with NTM pulmonary disease caused by MABC	
• Quality of Life – Bronchiectasis (QOL-B)• St. Georges Respiratory Questionnaire (SGRQ)• Patient-Reported Outcomes Measurement Information System Short Form v1.0 – Fatigue 7a Daily (PROMIS Short Form v1.0 – Fatigue 7a Daily)• Patient Global Impression of Change (PGI-C)• Patient Global Impression of Severity (PGI-S)• Clinical Global Impression – Severity of Illness (CGI-S)• Clinical Global Impression – Global Improvement Scale (CGI-I)• No new symptom (ie, symptom not present at baseline) with severity worse than mild
To evaluate the microbiological response of omadacycline in adult subjects with NTM pulmonary disease caused by MABC	
• Decrease in quantitative sputum culture at Day 84• Time to growth in liquid medium only• Time to first negative sputum culture

5 INVESTIGATIONAL PLAN

5.1 Overall Study Description

This is a Phase 2, double-blind, randomized, placebo-controlled, parallel-group, multi-center study in adults with NTM pulmonary disease caused by MABC. The study design is shown in [Figure 1](#).

Figure 1. Study Design Schema

Following a Screening period of up to 56 days (8 weeks) prior to dosing, eligible subjects will be randomized (1.5:1) to receive either 300 mg once daily oral omadacycline monotherapy or matching placebo. Subjects will be stratified according to their use of prior antibiotics for treatment of MABC NTM infection (received prior treatment vs. no prior treatment).

Subjects will attend monthly visits during the approximately 84 day (3-month) double-blind treatment period. In addition, subjects will complete a 14-day safety tele-visit as well as a safety follow-up call approximately 30 days after their last dose of test article. Total duration of subject participation is approximately 5 months.

Refer to the Schedule of Assessments for a complete summary of subject visits and assessments.

5.2 Rationale for Study Design

This study is intended to assess the safety and efficacy of omadacycline in addition to non-pharmacologic standard of care in NTM subjects caused by MABC. Non-pharmacologic measures, including patient education, airway clearance technique, inspiratory muscle training, and exercise training, are considered the first line of therapy in these subjects and will be permitted during the study ([Lan 2020](#)). A 3-month, monotherapy, placebo-controlled study design will allow the best assessment of omadacycline without any confounding

influence of other antibiotic treatments and will provide valuable, controlled data as well as adequate time to observe a treatment effect.

5.3 Approximate Duration of Study

The study is expected to be clinically complete in approximately 28 months.

5.4 Approximate Number of Subjects

Approximately 75 subjects (45 omadacycline and 30 placebo) will be enrolled at approximately 20 sites within the US.

6 STUDY POPULATION SELECTION

Each subject must participate in the informed consent process and sign and date an IRB/IEC/REB-approved informed consent form (ICF) before any procedures specified in this protocol are performed.

6.1 Study Population

This study will evaluate adult subjects with NTM pulmonary disease caused by MABC.

6.2 Inclusion Criteria

Subjects must meet all of the following criteria at Screening and/or Baseline to be eligible to participate in the study:

1. Written and signed informed consent must be obtained before any protocol-specific assessment is performed.
2. Male and female subjects age 18 years or older.
3. Diagnosed MABC pulmonary disease as per Infectious Diseases Society of America/American Thoracic Society guidelines criteria. Subjects must have:
 - At least 2 of the following NTM-infection symptoms at Screening and Baseline:
 - Chronic cough, coughing up blood (hemoptysis), wheezing, chest pain, frequent throat clearing, phlegm or sputum production, shortness of breath, fatigue, fever, night sweats, poor appetite, and/or weight loss
 - At least 1 positive pulmonary culture for MABC in the 6 months prior to Screening and 1 positive culture at Screening (note: prior culture and screening cultures must be at least 30 days apart).
 - Radiographic evidence of MABC infection via computed tomography (CT) scan of the chest within 3 months prior to Screening with findings consistent with NTM pulmonary disease. If no CT scan obtained within previous 3 months, one should be performed at Screening to confirm eligibility.
4. Based on the clinical assessment of the investigator, guideline-directed antibiotic therapy for treatment of MABC will not be required within the next 3 months, and a delay, in order for the subject to participate in a placebo-controlled clinical trial, is considered reasonable and clinically acceptable.
5. Be able to produce approximately 5 mL of sputum via spontaneous expectoration or be willing to undergo sputum induction to produce approximately 5 mL of sputum for microbiological evaluation.
6. Females must have a negative serum pregnancy test and agree to use a highly effective form of birth control (eg, abstinence, oral contraceptive, intrauterine device, or barrier contraception [eg, condom], tubal ligation, hysterectomy, bilateral oophorectomy, postmenopausal or vasectomized partner) from Screening through study completion. Males (if sexually active) must agree to use a highly effective method of birth control with female partner(s) from Screening through study completion.

7. Able and willing to adhere with the requirements and restrictions of the study.

6.3 Exclusion Criteria

Subjects meeting any of the following criteria at Screening and/or Baseline will be excluded from participation in the study:

1. Pregnant or nursing (breastfeeding) women.
2. Has received antibiotic treatment within 6 months prior to Screening for MABC or MAC.
3. Has received systemic or inhaled antibiotic therapy (other than chronic macrolide therapy) within 4 weeks prior to Screening.
4. Is experiencing an exacerbation of an infection with a non-*Mycobacterium* species (eg, *Pseudomonas aeruginosa*) that the investigator considers clinically relevant.
5. Has any of the following medical conditions:
 - Active pulmonary malignancy (primary or metastatic), or any type of malignancy requiring chemotherapy or radiation within 1 year prior to Screening.
 - Active allergic bronchopulmonary mycosis, or any other condition requiring chronic treatment with systemic corticosteroids (ie, prednisone dose \geq 15 mg/day for a period of \geq 4 consecutive weeks above this level; see [Appendix 2](#)) within 90 days prior to Screening.
 - Radiologic evidence of cavitary disease.
 - Known active pulmonary tuberculosis.
 - Cystic fibrosis.
 - History of lung transplantation.
 - Another advanced lung disease with a known percent predicted forced expiratory volume in 1 second $<$ 30%.
 - Disseminated or extra-pulmonary NTM disease.
6. Screening calculated creatinine clearance $<$ 30 mL/minute, using the Cockcroft-Gault equation ([Appendix 2](#)), requirement for any form of dialysis (eg, hemodialysis, peritoneal dialysis), or other evidence of severe renal disease.
7. Has any of the following at Screening:
 - Alanine aminotransferase or aspartate aminotransferase \geq 3 \times upper limit of normal.
 - Total bilirubin $>$ 1.5 \times upper limit of normal.
 - Suspected or confirmed clinical evidence of end-stage liver disease (eg, ascites, hepatic encephalopathy).
8. History of having experienced unstable cardiac disease (eg, unstable angina, myocardial infarction, acute congestive heart failure, unstable cardiac arrhythmia, etc.) within the 3 months prior to Screening.
9. Significant immunological disease determined by any of the following:
 - Current or anticipated neutropenia defined as $<$ 500 neutrophils/mm³.
 - Known infection with human immunodeficiency virus (HIV).

10. History of hypersensitivity or allergic reaction (eg, anaphylaxis, urticaria, other significant reaction) to any tetracycline (eg, minocycline, doxycycline, tigecycline, or omadacycline).
11. Has been previously treated with omadacycline.
12. History of pseudotumor cerebri, or prior (within 2 weeks prior to Screening) or planned concomitant use of isotretinoin.
13. Systemic treatment with disease-modifying antirheumatic agents, corticosteroids (equivalent to prednisone dose \geq 15 mg/day for a period of \geq 4 consecutive weeks above this level) or immunosuppressive agents in the 90 days prior to Screening.
14. Has current evidence of active pancreatitis.
15. Evidence or history of any other clinically significant medical condition or planned medical intervention that may, in the opinion of the investigator, pose a significant safety risk, impair study participation, impact the subject's ability to undergo the required study procedures or ability to complete the expected course of study treatment.
16. Any surgical or medical condition that, in the opinion of the investigator, might significantly alter the absorption, distribution, metabolism, or excretion of drugs.
17. Inability to fast for 4 hours prior to dosing and/or 2 hours after dosing.
18. Per discretion of the investigator, subject is not expected to survive the duration of the study.

6.4 Screen Failures

Subjects who sign the ICF but withdraw or are withdrawn from the study before random assignment to double-blind treatment are defined as screen failures. All screen failures should be recorded on the subject master list. Limited information including reason for screen failure will be recorded on the electronic case report form (eCRF) or interactive voice/web response system (IxRS) system for screen failures. Screen failure subjects may be re-screened at the discretion of the investigator and in consultation with the medical monitor as needed. Any subject who discontinues participation or is withdrawn before receiving a treatment assignment, and who is re-screened at a later time will be assigned a new subject number and recorded as re-screened.

7 STUDY TREATMENT(S)

7.1 Treatments Administered

[figure not shown]
Test articles will be supplied by Paratek Pharmaceuticals, Inc. (the sponsor). Test articles will be labeled according to regulations.

The test articles should be administered only to subjects who have provided informed consent and who meet all of the inclusion criteria and none of the exclusion criteria. Once the test article has been assigned to a subject, it must not be reassigned to another subject.

Following a Screening period of up to 56 days (8 weeks), eligible subjects will be randomly assigned to receive 300 mg oral omadacycline or matching placebo tablets.

7.2 Identity of the Investigational Product: Omadacycline

Oral Formulation (Omadacycline)

Name	Omadacycline Tablet, 150 mg
	

Placebo

Name	Placebo tablets
Excipients	Lactose monohydrate, microcrystalline cellulose, sodium stearyl fumarate
How supplied	Tablets are packaged in an alu/alu 6-count (2 x 3) foil blister. Secondary packaging will consist of fold-over, child-resistant blister cards (2 blisters per card) and patient kits containing 6 blister cards (72 tablets per patient kit)
Storage	Store at room temperature, 20°C to 25°C (68°F to 77°F); excursions permitted to 15°C to 30°C (59°F to 86°F) (see USP Controlled Room Temperature)
Preparation and handling	No special requirements
Administration	Please see Section 7.5

7.3 Dose Selection Rationale

The dosing regimen of omadacycline selected for this study is based on the demonstration of efficacy in a mouse model of *M. abscessus* pulmonary infection, as well as the totality of nonclinical and clinical experience to date, including in vitro antibacterial activity, PK characteristics, and the overall safety and tolerability profile of the FDA-approved dosing regimens for treatment of CABP and ABSSI.

In a nonclinical C3HeB/FeJ mouse model of *M. abscessus* pulmonary infection, omadacycline efficacy was demonstrated using the dose best representing the human equivalent exposure ie, area under the concentration-time curve (AUC) of the human 300 mg oral dose. The C3HeB/FeJ mouse was previously demonstrated to provide utility as a mouse model of *M. abscessus* pulmonary infection for antibacterial studies ([Maggioncalda 2020](#); [Story-Roller 2019](#)). Administration of a corticosteroid (dexamethasone) allows for initial proliferation of and subsequent sustained *M. abscessus* pulmonary infection and pathology following infection via an aerosolized route.

As detailed in the [Investigator's Brochure](#), the steady state AUC (hr* μ g/mL) for the 300 mg oral dose is 11.156, while the steady state free AUC (hr* μ g/mL) of the 300 mg oral dose is 8.92 (adjustment for free fraction by 20% human plasma protein binding; on file at Paratek). Therefore, a mouse dose was selected to represent a steady state free AUC (hr* μ g/mL) of approximately 9.

Omadacycline PK parameters in C3HeB/FeJ mice were determined after subcutaneous administration of omadacycline doses of 7.5, 15 and 30 mg/kg in order to calculate the appropriate mouse dose to study in the efficacy model. Following determination of key PK parameters, adjustment for free fraction in mice (33.9% mouse plasma protein binding; data on file at Paratek), and graphical assessment of the mouse free area under the concentration-time curve from time zero to 24 hours (AUC₀₋₂₄) (hr* μ g/mL) versus mouse doses studied, the resulting linear equation was utilized to calculate the appropriate mouse dose. Specifically, the data demonstrated that a mouse subcutaneous dose of approximately 15 mg/kg every 24 hours (q24h) best represents a human AUC₀₋₂₄ (hr* μ g/mL) of 9 (on file at Paratek).

The American Type Culture Collection (ATCC) reference strain *M. abscessus* 19977 (omadacycline minimum inhibitory concentration [MIC] values of 0.25 to 0.5 μ g/mL) and the clinical isolate M9501 (omadacycline MIC value of 0.25 μ g/mL) were evaluated in the mouse model of efficacy (MIC data on file at Paratek). Mice were infected via aerosolization and treatment was initiated 1-week post-infection. Mice were treated with either omadacycline (15 mg/kg q24h), imipenem (200 mg/kg every 12 hours; positive control) or vehicle (phosphate buffered saline; q24h) for 4 weeks and the bacterial burden in the lungs was evaluated at various timepoints (0, 1 week, 2 weeks, and 4 weeks) throughout the study. Efficacy was determined as a reduction in lung bacterial burden compared to vehicle controls.

M. abscessus lung burden in the vehicle control group increased throughout the course of infection as expected. In the positive control group (imipenem treatment), *M. abscessus* lung burden decreased gradually over the duration of the study. For mice infected with the

reference strain ATCC 19977, at the final timepoint of 4 weeks of treatment, omadacycline produced >3 log₁₀ reduction in total lung colony forming units compared to mice in the vehicle control group. Similarly, omadacycline treatment reduced lung burden of the clinical strain M9501 by 2 log₁₀ at the conclusion of 4 weeks of treatment.

Therefore, based on the demonstration of omadacycline efficacy in the mouse model of *M. abscessus* pulmonary infection at the equivalent human steady state free AUC (hr* μ g/mL) of approximately 9, the 300 mg oral dose will be evaluated in this human clinical study.

Phase 3 clinical trials in CABP and ABSSSI have demonstrated that omadacycline has an acceptable safety profile. Additionally, the 300 mg oral dose being used in this study has been approved by the FDA for these indications.

7.4 Description of Treatments

Subjects will be randomized (1.5:1) to 1 of the following treatment groups:

- Group 1: 300 mg oral omadacycline (2 \times 150 mg tablets administered once daily, q24h)
- Group 2: Placebo tablets resembling omadacycline (2 tablets administered once daily, q24h)

7.5 Test Article Administration

7.5.1 Oral Administration of Test Article

All doses of oral test article should be taken with water once daily, at approximately the same time of day.

All doses should be taken in a fasted state. Fasting is defined as no food, antacids or multivitamins containing multivalent cations (eg, aluminum, magnesium, calcium, bismuth, iron, or zinc) or drink except water for at least 4 hours before dosing. After dosing, no food or drink (except water) is permitted for 2 hours and no dairy products, antacids or multivitamins containing multivalent cations (eg, aluminum, magnesium, calcium, bismuth, iron, or zinc) for 4 hours.

7.6 Dose Adjustments and Interruptions of Test Article

No dose adjustments or planned interruptions of test article will be permitted during this study.

7.7 Method of Assigning Patients to Treatment Groups

All eligible subjects will be randomized via an IxRS that assigns them to the treatment group in a 1.5 to 1 ratio (omadacycline: placebo). The site delegate will contact the IxRS after confirming that the subject fulfills all the inclusion criteria and has none of the exclusion criteria. The IxRS will assign a test article to the subject based on a computer-generated

randomization schedule. The randomization will be a blocked randomization sequence stratified by prior antibiotic use for treatment of MABc NTM infection (prior antibiotic use and no prior antibiotic use) as defined in the IxRS specifications. Subjects randomized into the study will be assigned the treatment corresponding to the next available number from the computer-generated randomization schedule. The subject is considered randomized when the IxRS provides the test article assignment, regardless of whether the subject actually receives any test article.

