5. DETERMINATION OF SAMPLE SIZE

As the study is exploratory with respect to determination of efficacy, the sample size determination is provided to better ensure sufficient subjects are enrolled to provide an initial assessment of efficacy rather than test a specific hypothesis. With a randomization ratio of 1.5:1, a sample size of 75 subjects (45 omadacycline and 30 placebo) will provide approximately 80% power to detect an absolute treatment difference of 30% in clinical response rate at Day 84, based on clinical response rates of 15% and 45% in the placebo and omadacycline treatment groups respectively, using a Mantel-Haenszel test with 2-sided alpha level of .05.

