11.3 Adjustments for Covariates

The model for the primary efficacy and some secondary efficacy analyses will include adjustments for randomization stratification factor:

- Prior treatment of NTM caused by MABC at baseline status (received prior antibiotic treatment for NTM vs did not receive prior treatment for NTM)

If the sample size is too small in one of the randomization stratification subgroups such that an adjusted analyses cannot be performed, unadjusted analyses will be used

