Analyses will be conducted for both definitions of the primary endpoint. The number and percentage of subjects with a clinical response and without a clinical response will be presented by treatment group for the ITT analysis set. Exact 2-sided 95% CIs for the point estimates of the clinical response rates in each treatment group will be determined using the Clopper-Pearson method. The odds ratio (OR) (Omadacycline relative to Placebo) and p-value will be calculated using Cochran-Mantel Haenszel (CMH) test, stratified by prior antibiotic use. If the sample size is too small in one of the randomization stratification subgroups such that an adjusted analysis cannot be performed, an unadjusted analysis (chi-squared or Fisher's exact test) will be used.

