12.2.6 Clinical Global Impression-Improvement (CGI-I)

The sixth secondary efficacy endpoint is the CGI-I response at the Day 28, 56, and 84 visit, and Day 84/EOT. The number and percentage of subjects with each response will be presented by treatment group. The p-value from a Wilcoxon rank sum test will be provided.

An additional analysis of the CGI-I will summarize change from baseline as improved, no change and worsened at the Day 28, 56 and 84 visit, and Day 84/EOT. The number and percentage of subjects in each change category will be provided.

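### The SAP's unadjusted fallback for the stratified primary test has no workable trigger and should be deleted; CGI-I and CGI-S could keep the randomisation stratum at almost no cost

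*Protocol*

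**What the plan says.** Protocol 7.7 fixes the design: "The randomization will be a blocked randomization sequence stratified by prior antibiotic use". Protocol 12.5.1 specifies a CMH test stratified by this factor for clinical response, and protocol 12.5.2.2 does the same for the decrease in mycobacterial load. Neither section has a fallback.

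SAP 12.1.2 keeps the stratified CMH test as the default and then adds: "If the sample size is too small in one of the randomization stratification subgroups such that an adjusted analysis cannot be performed, an unadjusted analysis", which it names as chi-squared or Fisher's exact test. SAP 12.2.9 repeats this for the culture endpoint. SAP 11.3 has the general form: "such that an adjusted analyses cannot be performed, unadjusted analyses will be used". None of the three gives a number for too small, a rule for choosing between the two tests, or a time by which the choice is made. SAP section 14 reports no changes from the protocol analyses.

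For CGI-I, SAP 12.2.6 says: "The p-value from a Wilcoxon rank sum test will be provided". SAP 12.2.7 handles CGI-S in the same way. Protocol 12.5.2.1 already names the Wilcoxon test for the CGI outcomes. The ANCOVA (SAP 12.2) and both log-rank tests (SAP 12.2.10 and 12.2.11) include the stratum.

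**The concern.** The fallback depends on an event that hardly ever happens to a CMH test, because the method does not need a minimum stratum size. Read literally, the clause does nothing. Read loosely, it lets someone decide, possibly with results in view, which of three p-values to report for the primary endpoint.

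The SAP dates comparable decisions elsewhere: subgroup sizes are settled before database lock (11.6), and per-protocol exclusions before lock and unblinding (section 8). The primary test has no such date.

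The estimate is affected too. The estimand's summary measure is an odds ratio (SAP 12.1.2), but the fallback names only tests. Odds ratios are not collapsible, so dropping a prognostic stratum changes the quantity being estimated.

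The unstratified rank test for the CGI outcomes is a separate and smaller matter. It ignores a factor that the trial randomises by and that the other model-based and time-to-event analyses keep.

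**Working it through.** **Inputs from the documents.** Allocation: "assigns them to the treatment group in a 1.5 to 1 ratio (omadacycline: placebo" to 1 of 2 groups within 2 strata. Size: "a sample size of 75 subjects (45 omadacycline and 30 placebo) will provide approximately 80% power". Rates: "based on clinical response rates of 15% and 45% in the placebo and omadacycline treatment groups respectively". The test is Mantel-Haenszel at two-sided 0.05.

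**Assumptions (not in the documents).** The smaller stratum holds 3% to 50% of subjects, and the odds ratio for response between strata is 1 to 8. For CGI-I: 7 levels and a 0.7 SD treatment shift.

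**1. The plan's own figure.** The pooled rate is (45 × 0.45 + 30 × 0.15)/75 = 0.33.
- SE under the null = √[0.33 × 0.67 × (1/45 + 1/30)] = 0.1108
- SE under the alternative = √[0.45 × 0.55/45 + 0.15 × 0.85/30] = 0.0987
- Power = Φ[(0.30 − 1.96 × 0.1108)/0.0987] = Φ(0.838) = 79.9%

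The stated 80% reproduces. Exact enumeration of all 46 × 31 outcomes, ignoring strata, gives Mantel-Haenszel 80.2%, Pearson chi-squared 81.6% and Fisher 77.2%. At these sizes Pearson rejects whenever Fisher does, so the two disagree in 81.6 − 77.2 = 4.4% of trials.

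**2. Can a small stratum stop the CMH test?** In each stratum let a be the responders on omadacycline, n₁ and n₂ the arm sizes, m the total responders and N the stratum size. The stratum adds a − n₁m/N to the numerator and n₁n₂m(N − m)/[N²(N − 1)] to the variance.
- One arm only (n₂ = 0): a = m and n₁ = N, so both terms are 0.
- One outcome only (m = 0 or m = N): both terms are 0.
- A single subject: the stratum is skipped.

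Example: the main stratum has 19/43 against 5/30 responders, and the small stratum has 1/2 against 0/0.
- Main stratum: expected 43 × 24/73 = 14.14; variance 43 × 30 × 24 × 49/(73² × 72) = 3.954; statistic (19 − 14.14)²/3.954 = 5.98.
- Small stratum: adds 0 to both.
- The CMH statistic is 5.98 with or without it.

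The Mantel-Haenszel odds ratio, a ratio of sums over strata, also receives zero from a one-arm stratum. The CMH test fails only if the variance is zero in every stratum, for example if nobody responds. In that example Pearson fails as well.

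**3. What the fallback costs.** Simulation with 200,000 trials per setting, overall rates held at 45% and 15%:

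| Small stratum (active + placebo) | Stratum odds ratio | CMH | Chi-squared | Fisher |
|---|---|---|---|---|
| 2 (1+1) | 1 | 80.3% | 81.4% | 77.0% |
| 2 (1+1) | 8 | 81.4% | 80.7% | 76.2% |
| 5 (3+2) | 1 | 80.9% | 81.6% | 77.2% |
| 5 (3+2) | 8 | 83.9% | 82.4% | 77.9% |
| 7 (4+3) | 1 | 80.9% | 81.6% | 77.3% |
| 7 (4+3) | 8 | 84.3% | 81.5% | 76.9% |

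For strata of 2 to 7 subjects, CMH minus chi-squared runs from 80.3 − 81.4 = −1.1 to 84.3 − 81.5 = +2.8 points. CMH minus Fisher runs from 80.3 − 77.0 = +3.3 to 84.3 − 76.9 = +7.4 points. About 3 of those points (80.2 − 77.2) arise with no strata at all. At a common response rate of 27%, simulated type I error in these settings was 4.8–5.0% for CMH, 3.9–5.0% for chi-squared and 2.7–3.7% for Fisher.

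**4. What the odds ratio means.** The crude odds ratio is (0.45/0.55)/(0.15/0.85) = 4.64. With an assumed stratum log-odds of 1.5, the within-stratum odds ratio that gives the same overall rates is about 4.8 at a 4% stratum share, 5.0 at 10% and 5.5 at 50%.

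**5. CGI-I and CGI-S.** Change in power from replacing Wilcoxon with van Elteren, by simulation: about −1 to 0 points if the stratum is not prognostic, 0 to +2 at a 0.5 SD gap between strata, and +1 to +8 at 1 SD. At 1 SD the Wilcoxon type I error falls to 3.3–3.9%.

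**The case against.** The strongest reply is that the stratified CMH test is the primary analysis and the fallback applies only if an adjusted analysis cannot be performed. If that almost never happens, the clause costs nothing, and harm requires the sponsor to depart from its own wording. That stands against any claim of a certain loss. It does not explain why the clause should stay.

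A reader might infer that the plan discards the stratum and loses power for no reason. The documents do not support that. Stratification is the default. With a very small stratum, chi-squared loses little and can gain about a point. The larger gaps appear with bigger prognostic strata: at a stratum odds ratio of 8 and a stratum of 15 of 75 or more, CMH gains 3 to 5 points over chi-squared and 8 to 10 over Fisher. Nobody could say there that CMH cannot be performed. A reader might also infer an inflated false-positive rate, but the simulated sizes in the working are at or below about 5% for each test.

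An exact stratified test for sparse data would not be a clean remedy. It brings another undefined trigger, and in a simulation with strata of 3 to 8 subjects its power was 76.6–79.1%, close to Fisher's 76.6–78.7%.

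All p-values are nominal (SAP section 6), which limits the consequence. It does not make an undefined choice of test for the primary endpoint good practice, since the SAP presents its analyses as fixed before unblinding.

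On CGI-I, the unstratified test is in the protocol, so it is not a SAP departure, and the stated power does not rest on it. PGI-C and PGI-S also use unstratified Fisher tests (SAP 12.2.4 and 12.2.5). Both observations are correct, and they make the CGI change an improvement, not a correction.

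**Conclusion.** The point holds as a gap in specification with a modest power cost. The fallback has no trigger that a small stratum would meet. If used at discretion, it leaves the choice of test and the odds-ratio estimator open. It is an addition to the protocol that SAP section 14 does not acknowledge. The cost is about −1 to +3 points if chi-squared is chosen and about 3 to 7 points if Fisher is chosen, for strata of 2 to 7 subjects. Only Fisher falls below the stated 80% before any stratum effect, at 77.2%.

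The text, the reproduced 80% and the algebra of the CMH statistic are firm. The stratum split and its prognostic strength are assumed. The eligibility criteria bar recent MABC or MAC antibiotics but do not determine how many subjects were treated earlier. The CGI gains also rest on an assumed scale and effect, and they vanish if prior antibiotic use is not prognostic.

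**What to change.** 1. Delete the unadjusted fallback in SAP 11.3, 12.1.2 and 12.2.9. Always report the stratified CMH p-value with the Mantel-Haenszel odds ratio.
2. Do not replace it with an open-ended exact test for sparse data. If any alternative is kept, name one test, make the trigger objective (the CMH statistic is not computable), fix it before unblinding, and list it in SAP section 14.
3. In SAP 12.2.6 and 12.2.7, replace the Wilcoxon test with the van Elteren test stratified by prior antibiotic use. Because protocol 12.5.2.1 names the Wilcoxon test, record this change in section 14 too.

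The cost is a few lines of SAP wording and minor programming. No subjects or new data are needed.
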